6.6.2.1. Palliative Surgery and Radiation Therapy While on Study Treatment

Guidance regarding palliative surgery and radiation therapy while on study treatment is as follows:

- Palliative radiation: any use of palliative radiation should not involve target lesions and should be discussed and agreed upon with the study medical monitor. Study treatment should be withheld for at least 1 week before, during, and 1 week after radiation. Participants should be closely monitored for any potential acute toxicity during and after receiving radiotherapy, and AEs should resolve to \leq Grade 1 prior to resuming immunotherapy agents.

- Palliative surgical procedures: permitted for the underlying medical condition and management of symptoms but should not involve target lesions. Study treatment adjustments and safety washout periods should be discussed and agreed upon with the study medical monitor based on the extent and nature of surgery.

Other restrictions and precautions include the following:

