10.4. Statistical Analyses

10.4.1. Primary Analysis

Progression-free survival, defined as the time from the date of randomization to the date of the first documented progression or death due to any cause, whichever occurs first. Progression-free survival will be based on investigator assessment per RECIST v1.1. Survival data will be analyzed by the Kaplan-Meier method, treating participants with no observed death or disease progression as censored. Censoring for PFS will follow the primary analysis algorithm outlined in Table 20, which is based on regulatory guidelines (FDA 2015).

Table 20: Evaluation and Censoring of Progression-Free Survival

Situation	Primary Analysis	Sensitivity Analysis 1	Sensitivity Analysis 2
No valid postbaseline response assessments in the absence of death prior to first scheduled tumor assessment	Censored at date of randomization	Censored at date of randomization	Censored at date of randomization
Progression documented between scheduled visits	Progressed at date of first overall response of PD	Progressed at date of first overall response of PD	Progressed at date of first overall response of PD
Death before first PD assessment	Progressed at date of death	Progressed at date of death	Progressed at date of death
No PD and no death; new anticancer treatment is not initiated	Censored at last disease assessment	Censored at last disease assessment	Censored at last disease assessment if still on study therapy; progressed at treatment discontinuation otherwise
No PD and no death; new anticancer treatment is initiated	Censored at last disease assessment before new anticancer treatment	Censored at last disease assessment before new anticancer treatment	Progressed at date of new anticancer treatment
No PD and no death; after ≥ 2 missed disease assessments	Censored at last disease assessment prior to the ≥ 2 missed disease assessment	Censored at last disease assessment	Censored at last disease assessment

Table 20: Evaluation and Censoring of Progression-Free Survival (Continued)

Situation	Primary Analysis	Sensitivity Analysis 1	Sensitivity Analysis 2
PD or death documented after ≤ 1 missed disease assessment	Progressed at date of documented PD or death	Progressed at date of documented PD or death	Progressed at date of documented PD or death

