Note 2: The date on which any participant received high-dose palliative radiotherapy to sites of known disease that have been selected as target or nontarget lesions will be censored for PFS on the day the first fraction was delivered. Participants who receive a single fraction of radiotherapy to a single site of known bone metastasis will not be censored for PFS.

The nominal 1-sided p-value from the stratified log-rank test will be reported, stratified for LAG-3 expression status ($\geq 5\%$ vs $< 5\%$), PD-L1 CPS (1%-19% vs $\geq 20\%$), and HPV p16 status (p16-positive vs p16-negative). The strata identified in the randomization process will be used for the analysis.

The HR and its 95% CI will be estimated based on the stratified Cox regression model using the same stratification factors as for the log-rank test with Efron's method accounting for ties in event times (1977).

Kaplan-Meier curves for PFS will be presented by treatment groups. The Kaplan-Meier estimate of median PFS will be presented with its 95% CI. The 95% CI will be calculated using the generalization of Brookmeyer and Crowley's method (1982) with log-log transformation (Klein and Moeschberger 1997).

To evaluate the robustness of the PFS endpoint per RECIST v1.1 based on investigator review, a sensitivity analysis will handle participants who miss more than 1 disease assessment indifferently from participants who miss 0 or 1 disease assessment (ie, the status depends on if there is PD or death) and will handle participants who discontinue treatment or initiate an anticancer treatment after discontinuation of study treatment differently from the primary analysis. The censoring rules for the sensitivity analyses are also summarized in Table 6. Within each analysis, if a participant meets multiple criteria for censoring, the censoring criterion that occurs earliest will be applied.

The reverse Kaplan-Meier method will be used to estimate the median PFS follow-up time, presented with its 95% CI. The 95% CI will be calculated using the generalization of Brookmeyer and Crowley's method (1982) with log-log transformation (Klein and Moeschberger 1997).

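### SAP Table 6 Note 2 censors PFS at high-dose palliative radiotherapy, but the Protocol permits such treatment away from target lesions and has no matching censoring rule; no analysis set out in the SAP shows the effect

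*SAP*

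**What the plan says.** **SAP 7.3.2, Table 6 Note 2.** Any participant who "received high-dose palliative radiotherapy to sites of known disease that have been selected as target or nontarget lesions will be censored for PFS"; the date used is the day of the first fraction. There is one exemption: "Participants who receive a single fraction of radiotherapy to a single site of known bone metastasis will not be censored for PFS". The note stands under the whole table and is not limited to the primary column. The same section adds that "if a participant meets multiple criteria for censoring, the censoring criterion that occurs earliest will be applied", so follow-up after the first fraction does not bring the participant back into the risk set.

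**Protocol 6.6.2.1.** Palliative radiation is permitted on study with one anatomical limit: "any use of palliative radiation should not involve target lesions and should be discussed and agreed upon with the study medical monitor". Study drug is paused, not stopped: "Study treatment should be withheld for at least 1 week before, during, and 1 week after radiation". Adverse events must settle "prior to resuming immunotherapy agents", so resumption is foreseen.

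**Protocol 8.2.1.2.** The listed reasons to stop imaging are PD, new anticancer treatment, withdrawal of consent, death and end of study. Palliative radiotherapy is not named.

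**Protocol 10.4.1, Table 20.** No row or note mentions radiotherapy. The row "PD or death documented after ≤ 1 missed disease assessment" counts the participant as progressed at the date of PD or death. The row on new anticancer treatment covers only participants with neither PD nor death.

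**SAP change record.** SAP 10.1 reports that the PFS censoring rule was updated in line with FDA guidelines, without mentioning radiotherapy. SAP 10.2 says Table 6 was brought into line with the Protocol.

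**The concern.** The same participant can have two different primary outcomes, depending on which document the programmer follows. Someone who has multi-fraction, high-dose palliative radiotherapy to a nontarget lesion, resumes study drug, keeps being scanned and then progresses is an event under Protocol Table 20 and a censored observation under SAP Note 2.

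This matters because the censoring may be informative. If lesions that need palliative radiation tend to be close to progression, which is plausible although the documents do not say so, Note 2 removes participants just before their event. When the groups are irradiated equally often, little changes except the event count. When they are not, the group with more radiotherapy loses more events and its hazard looks lower. More use in TG1 pulls the HR toward 1; more use in a combination group flatters the combination.

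The analyses described in the SAP would not show this. The Table 6 sensitivity column changes the handling of missed assessments, treatment discontinuation and new anticancer therapy. SAP 7.3.4 deals with stratification errors and an unstratified model. DOR inherits the rule, because SAP 7.4.3 applies the PFS censoring algorithm. The text of SAP 7.5 (exploratory analyses) is not visible in the public version, so this statement covers the visible plan only.

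**Working it through.** **Step 1: the rules side by side.** Let R be the first fraction of high-dose palliative radiotherapy to a nontarget lesion, and P > R the later PD or death, with no new anticancer therapy and at most one missed scan.

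| | Status | Time |
|---|---|---|
| Protocol Table 20 | event | P |
| SAP Table 6 with Note 2, either column | censored | R |

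If PD comes before R, it is an event in both. If the radiotherapy is not high-dose, or meets the bone exemption, or is given to a site not selected as a target or nontarget lesion, Note 2 does not apply and the documents agree.

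**Step 2: reproduce the design figures.** Inputs from SAP 3.2 and Protocol Table 17: 94 events per pair, HR 0.6, 1:1 within a pair, one-sided alpha 0.05, TG1 median 3 months, 12 months of accrual plus 8 of follow-up, 1% annual dropout, 54 per group.

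Power = Φ(√d/2 × |ln HR| − z)

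- Alpha 0.05: √94/2 × 0.5108 − 1.6449 = 2.4763 − 1.6449 = 0.831, so power is 79.7% (SAP Table 2: 80.0%).
- Alpha 0.10: 2.4763 − 1.2816 = 1.195, so power is 88.4% (SAP Table 2: 88.4%).
- Exponential PFS with these inputs gives 51.0 + 45.1 = 96.1 expected events per pair at month 20, and 51.0 + 2 × 45.1 = 141.2 over three groups. These agree with the planned 94 and 140.

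The sample size is not in question.

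**Step 3: loss of events alone.** Assume a share f of the 94 events is lost to Note 2, the HR stays at 0.6 and the cut-off is not delayed.

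| f | Events, 94 × (1 − f) | Power, one-sided 5% |
|---|---|---|
| 0 | 94 | 79.7% |
| 2% | 92.1 | 79.0% |
| 5% | 89.3 | 77.9% |
| 10% | 84.6 | 75.9% |
| 15% | 79.9 | 73.8% |

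**Step 4: loss of events plus informative censoring.** Assumptions: a share of each group is irradiated before PD and censored then; true HR 0.6; unstratified model. The Cox column comes from 3,000 to 4,000 simulated pairs per scenario, with radiotherapy at a uniform time before PD or 1 month before it. The rate-ratio column is a large-sample approximation with radiotherapy 0.5 months before PD. A dash means not computed or not reported.

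| Irradiated, TG1 / combination | Events | HR, Cox | HR, rate ratio | Power |
|---|---|---|---|---|
| 0 / 0 | 96 | – | 0.60 | about 80% |
| 5% / 5% | 91–92 | – | 0.60 | 79% |
| 10% / 10% | 86–87 | – | 0.60 | 77–78% |
| 15% / 15% | 82 | – | – | 76% |
| 10% / 5% | – | 0.61–0.62 | 0.63 | 70–74% |
| 15% / 5% | – | 0.63–0.65 | 0.66 | 61–68% |
| 5% / 10% | – | 0.57–0.58 | 0.57 | – |
| 5% / 15% | – | – | 0.54 | – |

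Equal use costs 80 − 79 = 1 to 80 − 76 = 4 points. Step 3 gives a slightly larger loss at 15% (79.7 − 73.8 = 5.9) because it starts from 94 events instead of 96 and holds the HR at exactly 0.6. Unequal use shifts the HR by between 0.61 − 0.60 = 0.01 and 0.66 − 0.60 = 0.06 one way, and by up to 0.60 − 0.54 = 0.06 the other.

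With a true HR of 1.0 and use of 5% in TG1 versus 15% in a combination group, the apparent HR is 0.92–0.94 (Cox) or 0.90 (rate ratio), and the one-sided 5% test rejects in 8–11% of simulated pairs. With 15% versus 5%, the rate ratio is 1.11.

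**The case against.** Several points on the other side are sound.

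- **Scope.** A reader might infer that the SAP censors all palliative radiotherapy to nontarget lesions. It does not: the rule is confined to high-dose treatment of selected lesions and has the bone exemption. The conflict affects a subset of what the Protocol permits. How large a subset cannot be said, because high-dose is undefined.
- **Protocol silence.** A reader might infer that Table 20 expressly counts PD or death after radiotherapy. It does so only by default; the row that applies is about missed scans. Protocol 6.6.3 also bars radiotherapy for tumor control, and neither document says whether high-dose treatment of measured disease falls under that bar or counts as new anticancer treatment. If it did count as new anticancer treatment, scheduled imaging would stop at its start. Even so, the Table 20 row for new anticancer treatment would not remove a PD or death that was recorded.
- **Disclosure.** A reader might infer that the change was hidden. SAP 10.1 does report a PFS-censoring update, only without radiotherapy. Protocol Section 10 requires an amendment for changes to primary methods but also leaves detail to the SAP, so whether Note 2 needed an amendment is arguable.
- **Choice of rule.** Radiation can delay visible progression in a nontarget lesion, so counting the later event carries its own bias. The documents do not show that Note 2 is the wrong primary rule.
- **Weight.** The rates and imbalances above are assumed. SAP Table 3 already tabulates 82 and 87 events per pair. More radiotherapy in TG1 biases against superiority. SAP 10.2 removed Type I error control, so the p-value is nominal.

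The last point lowers the importance of power but not of the HR and its interval, which remain the main result. None of these points removes the mismatch or supplies an analysis that would reveal its effect.

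**Conclusion.** The point holds in limited form. For high-dose palliative radiotherapy that avoids target lesions and is outside the bone exemption, PD or death afterwards is an event under the Protocol by default and censored under the SAP. The SAP change record does not name the rule, and its statement that Table 6 was aligned with the Protocol does not fit Note 2. No visible analysis relaxes it.

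The size cannot be derived from the documents. With 5–15% irradiated, equal use is a minor loss. Unequal use biases the primary HR by roughly 0.01 to 0.06 around 0.6, in whichever direction the imbalance runs. A reader might conclude that the primary result will be biased, or that the primary rule must be reversed. Neither follows: no imbalance is documented, and each rule has a cost. What the documents do support is that the two texts must agree and that the effect of the rule should be visible.

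**What to change.** 1. Reconcile SAP Table 6 Note 2 with Protocol Table 20 and Protocol 6.6.2.1, and name the radiotherapy rule in SAP 10.1.
2. Define high-dose for the analysis, and state whether palliative radiotherapy counts as new anticancer treatment in Table 6.
3. Report PFS both ways: PD or death after Protocol-permitted radiotherapy counted as an event in one analysis, and censored at the first fraction in the other. State in advance which is primary. Table 20 as written implies that the event is counted; if Note 2 stays primary, amend Table 20. Handle DOR the same way.
4. Tabulate, by treatment group, the number of participants censored for radiotherapy and how many had PD or died afterwards.

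Cost: SAP wording, one extra PFS run (with the matching DOR run) and one small table, plus a Protocol amendment only if Note 2 stays primary. In the version that counts the event, an irradiated nontarget lesion may show PD later; reporting both versions makes that visible too.

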10. STATISTICS

This section outlines the statistical analysis strategy and procedures for this study. If changes are made to primary efficacy and safety and/or secondary efficacy hypotheses or the statistical methods related to those hypotheses after the study has begun, but before the final database lock, the Protocol will be amended, consistent with ICH E9 (1998) and ICH E9 (R1; 2021). The detailed statistical analyses will be documented in the Statistical Analysis Plan.

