10.1. Sample Size Determination

The sample size calculation is based on the primary endpoint of PFS. Approximately 162 participants will be randomized in a 1:1:1 ratio into TG1:TG2:TG3. The study is event-driven and will be complete after approximately 94 PFS events have been observed between TG1 and TG2 or between TG1 and TG3 (approximately 140 PFS events across the 3 treatment groups). Based on a target of 94 PFS events for all participants at the final analysis between TG1 and TG2 or between TG1 and TG3 (approximately 140 PFS events across the 3 treatment groups), which is expected to occur about 20 months from the start of enrollment, the study has approximately 80% power to detect an HR of 0.6 at an overall alpha level of 5% (1-sided) favoring one of the combination therapies with the assumption of study parameters as specified in Table 17 for PFS.

The sample size and power calculations were performed in R package "gsDesign."

Table 17: Sample Size Assumptions for Progression-Free Survival

Variable	Assumptions
Median PFS in TG1 (All participants)	3 months ^a
Randomization ratio	1:1:1
Assumed HR (All participants)	0.6
Enrollment duration	12 months
Follow-up for PFS	8 months
Assumed annual dropout rate	1%

^a Burtneess et al 2019.

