10.3. Level of Significance

For the primary endpoint, the overall 1-sided alpha level will be strongly controlled 10%, with an initial 1-sided alpha allocation for each hypothesis at 5% (refer to SAP). The detailed multiplicity control will be specified in the Protocol Section 10.6. Unless otherwise stated, all CIs provided will be reported at a 95% confidence level.

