PD or death documented after ≥ 2 missed disease assessments	Censored at last disease assessment prior to the ≥ 2 missed disease assessment	Progressed at date of documented PD or death	Progressed at date of documented PD or death

The stratified log-rank test will be used to compare PFS between treatment groups in the ITT at a 1-sided 5% significance level, stratified for LAG-3 expression status ($\geq 5\%$ vs $< 5\%$), PD-L1 CPS (1%-19% vs $\geq 20\%$), and HPV p16 status (p16-positive vs p16-negative, oropharyngeal only). The strata identified in the randomization process will be used for the analysis.

The HR and its 95% CI will be estimated based on the stratified Cox regression model using the same stratification factors as for the log-rank test with Efron's method accounting for ties in event times (1977).

Kaplan-Meier curves for PFS will be presented by treatment groups. The Kaplan-Meier estimate of median PFS will be presented with its 95% CI. The 95% CI will be calculated using the generalization of Brookmeyer and Crowley's method (1982) with log-log transformation (Klein and Moeschberger 1997).

Since disease progression is assessed periodically, PD can occur any time in the time interval between the last assessment at which PD was not documented and the assessment when PD is documented. In order to evaluate the robustness of the PFS endpoint per RECIST v1.1 based on investigator review, 2 sensitivity analyses with a different set of censoring rules will be performed. For the first sensitivity analysis, participants who miss more than 1 disease assessment are not handled differently from participants who miss 0 or 1 disease assessment (ie, the status depends on if there is PD or death).

The second sensitivity analysis handles participants who discontinue treatment or initiate an anticancer treatment subsequent to discontinuation of study-specified treatments differently from the primary analysis. The censoring rules for these 2 sensitivity analyses are also summarized in Table 20. Within each analysis, if a participant meets multiple criteria for censoring, the censoring criterion that occurs earliest will be applied.

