10.6. Multiplicity Control

The study uses the graphical method of Maurer and Bretz ([Maurer and Bretz 2013](#)) to strongly control type I error for multiple hypotheses. A graphical display of the plans for reallocation of alpha is displayed in [Figure 7](#) using the initial 1-sided alpha allocation for each hypothesis in the ellipse representing the hypothesis. The weights for reallocation from each hypothesis to the others are represented in the boxes on the lines connecting the hypothesis. The detailed information for each hypothesis about the bounds and boundary properties for the final analysis for different alpha level due to the alpha reallocation will be tabulated in SAP.

Figure 7: Multiplicity Graph for 1-Sided Alpha Reallocation Strategy

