10.1. Changes to Protocol-Defined Analyses

The following changes were made in the original SAP:

- Clarification was provided to depict that the overall alpha level is strongly controlled at 10% (1 sided). Furthermore, it was clarified that the alpha level of 5% is used when comparing one combination therapy versus TG1.
- The number of PFS events was updated to 94 (see [Table 2](#)) and the approximate number of PFS events (140) across 3 treatment groups was added.
- The ADA evaluable population was added.
- The censoring rule for PFS was updated to align the situations with the primary analysis algorithm-based on FDA guidelines. A sensitivity analysis, which applied alternative censoring rules for PFS, is no longer needed.
- The classification variable, "Region (North America, EU, or Asia)," was added for subgroup analysis.

The following updates were made for SAP Amendment 1:

- Added boundary properties for scenarios when the number of PFS events is approximately 108, 123, and 130 across the 3 treatment groups if the primary analysis is conducted after the last participant has been followed up for at least 8 months after randomization.
- Added analysis of the difference in ORR and DCR between TG2 and TG1 and between TG3 and TG1.
- Updated the OS analysis to only provide estimates of median OS, its 95% CI, median follow-up time for OS, and HR. The number of OS events at the final analysis does not support a valid comparison between treatment groups, and the study is not powered for OS comparison. No formal statistical testing will be conducted.

The following updates were made for SAP Amendment 2:

- Updated ORR and DCR analysis to show only the differences in ORR or DCR between treatment groups and the corresponding 95% CIs. Odds ratio and 95% CI will not be provided, as the difference is more easily interpretable.

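### The Protocol promises strong 1-sided error control for the two primary PFS hypotheses, the SAP has withdrawn it without a Protocol amendment, and the Protocol states two different overall alpha levels

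*SAP*

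**What the plan says.** **Protocol.** Section 10.3 states that "the overall 1-sided alpha level will be strongly controlled 10%, with an initial 1-sided alpha allocation for each hypothesis at 5" percent, and refers to the SAP. Section 10.4.1 sets the test level: "The stratified log-rank test will be used to compare PFS between treatment groups in the ITT at a 1-sided 5% significance level". Section 10.6 adopts a graphical procedure "to strongly control type I error for multiple hypotheses" and says that the SAP will tabulate the bounds at the alpha levels that reallocation can produce. Section 10.1 describes the power as holding "at an overall alpha level of 5% (1-sided) favoring one of the combination therapies". The opening of section 10 covers changes to the primary hypotheses or their methods made after the study has begun, "but before the final database lock, the Protocol will be amended".

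**SAP.** Section 7.2 keeps both superiority hypotheses: H1 (TG3 against TG1) and H2 (TG2 against TG1). Tables 2 and 3 still give bounds at 1-sided 0.05 and 0.10. For the primary analysis, section 7.3.2 says: "The nominal 1-sided p-value from the stratified log-rank test will be reported". No analysis section gives a level, an allocation, a reallocation or a criterion for success.

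The SAP 10.2 entry for Amendment 1 (12 DEC 2024) records that Type I error control was taken out because the study is not registrational and alpha had served only to size it. SAP 10.1, which lists departures from Protocol-defined analyses, has an Amendment 1 entry that omits this change. SAP 2.1 names Protocol Amendment 2 (19 DEC 2023) as its basis. That version still promises control, and the documents contain no later one.

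**The concern.** The primary objective is answered by two comparisons that share the TG1 control. The Protocol tells the reader how each will be judged and sends them to the SAP for the details. The SAP no longer holds those details. It leaves a p-value without a threshold and two columns of bounds that nothing links.

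Three things are at stake:

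- A reader of the Protocol will credit the PFS result with an error-rate property that the SAP has dropped.
- At 94 events, an observed HR between the two tabulated bounds, say 0.74, passes one column and fails the other. Which column applies depends on a rule that the SAP does not state.
- The Protocol's own account is inconsistent. Section 10.1 makes 5% the overall level; section 10.3 makes it 10%.

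**Working it through.** **1. Inputs.** 94 events per pairwise comparison, HR 0.6, 1-sided alpha 0.05 or 0.10 (SAP 3.2 and Table 2); 1:1:1 allocation; two hypotheses with a common control (SAP 7.2).

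**2. The plan's own figures.** The HR at the bound is approximately exp(−2z/√d), and power is approximately Φ(√(d/4)·|ln HR| − z). With d = 94, √(94/4)·|ln 0.6| = 4.848 × 0.511 = 2.476.

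| 1-sided alpha | z | HR at bound, here | Table 2 | Power, here | Table 2 |
|---|---|---|---|---|---|
| 0.05 | 1.645 | 0.712 | 0.7120 | Φ(0.831) = 0.797 | 0.8000 |
| 0.10 | 1.2816 | 0.768 | 0.7670 | Φ(1.195) = 0.884 | 0.8840 |

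The design figures reproduce, so the sizing is not in question. The 80% power belongs to a single comparison at 5%. The 5% in Protocol 10.1 is therefore a per-comparison level, and calling it overall is an error.

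**3. Familywise error when both nulls are true.** With equal groups and a shared control, the two test statistics have correlation about (1/n)/(2/n) = 0.5. The chance of at least one false positive is 1 − P(Z₁ < z, Z₂ < z).

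| Threshold for each test | Correlation 0.5 | If independent | Upper limit (sum) |
|---|---|---|---|
| 0.05 | 8.8% | 9.75% | 10% |
| 0.10 | 16.8% | 19% | 20% |

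At 0.05 each, the Protocol's 10% holds whatever the correlation. At 0.10 each from the start, it does not.

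**4. What the Protocol rule would deliver.** The reallocation weights are in Figure 7, which is not shown in the text available. Assume full reallocation: after one rejection, the other hypothesis is tested at 0.10. The 0.10 column of Table 2 fits that assumption. By simulation at 94 events and correlation 0.5:

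- Familywise error is 8.8% if both arms are null, and 9.8% if one is null and the other has HR 0.6. Both are within 10%.
- If both arms have HR 0.6, power is about 85% for each hypothesis, 91% for at least one and 80% for both. Without reallocation, power for each is 79.7% (step 2).

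Dropping reallocation alone therefore costs power and does not inflate error. What the SAP has lost is the stated threshold and the reallocation step.

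**The case against.** The strongest reply is that the removal was deliberate and explained. This is a Phase 2 study, the sponsor says that alpha served no decision, Protocol 10.4.3 rests efficacy conclusions on the totality of the endpoints, and calling the p-value nominal signals that no confirmatory claim is intended. That stands as a reason for the choice, and it makes withdrawing the Protocol claim as legitimate as restoring the rule. It does not reconcile the documents. Protocol 10.3, 10.4.1 and 10.6 give alpha a role in testing, not only in sizing, and section 10 requires an amendment for such a change.

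Four stronger readings are tempting, and the documents do not support them:

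- *The SAP inflates familywise error above 10%.* This needs 0.10 for both tests from the outset. Protocol 10.4.1 sets 5%, SAP 3.2 powers each comparison at 5%, and the title of Table 2 presents its columns as possible alpha levels, which fits reallocation. The fair statement is that the SAP does not exclude such a reading.
- *SAP 10.1 and 10.2 contradict each other.* The 10% statement in 10.1 records a change made in the original SAP; the removal in 10.2 belongs to Amendment 1. These are successive history entries. The valid point is that 10.1 omits the removal.
- *The 95% CI is wrong because it does not match a 1-sided 5% bound.* The SAP follows Protocol 10.3 and 10.4.1, which specify 95% intervals.
- *The trial has no success rule at all.* That describes the SAP only. The unamended Protocol still has one.

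**Conclusion.** The point holds as a conflict between governing documents on how the primary endpoint is judged. The Protocol claims strong 1-sided control at 10%. The SAP implements none, the Protocol has not been amended, and SAP 10.1 does not list the departure. Separately, Protocol 10.1 misstates the overall alpha as 5%.

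The numerical consequence is modest on the natural reading: 8.8% at 0.05 per test. The 16.8% figure shows what the missing rule leaves open, not what the SAP prescribes. The familywise figures assume correlation 0.5 from equal allocation and a shared control. The figures for the restored rule also assume full reallocation, which must be checked against Figure 7. That no later Protocol amendment exists is judged from the documents supplied.

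**What to change.** Before unblinding, take one of two routes.

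**(a) Restore the rule.** State in SAP 7.3.2 that H1 and H2 are each tested at 1-sided 0.05, with reallocation as in Protocol Figure 7. If the figure confirms full reallocation, the second test after a rejection uses 0.10. Add a new SAP change entry that supersedes the removal.

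**(b) Withdraw the claim.** Amend Protocol 10.3, 10.4.1 and 10.6 to remove the control claim, list the change in SAP 10.1, and label the PFS comparisons as descriptive.

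Under either route, correct Protocol 10.1 to 5% (1-sided) per comparison; under (a), add 10% overall. Keep the existing SAP 10.2 entry, since it is a true record of what was done. A 90% CI for the HR beside the 95% CI would match the 1-sided 5% bound, but it is optional.

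The cost is drafting. Route (a) needs SAP wording and one corrected Protocol sentence; route (b) needs a Protocol amendment and one SAP entry. The bounds at 94 events are already tabulated. Neither route changes the number of participants, the event target or the data collected.
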